3.6 RATIONALE FOR STUDYING GOAT AS A NOVEL TARGET TO TREAT AUD

After the discoveries of GHS-R1a (Howard et al., 1996) and then acyl-ghrelin (Kojima et al., 1999), identifying the system in charge of ghrelin's octanoylation was key, as acyl-ghrelin but not DAG binds with high affinity to GHS-R1a. Independent efforts from the Goldstein & Brown (Gutierrez et al., 2008) and Eli Lilly (Lim, Kola, Grossman, & Korbonits, 2011) labs led to the discovery of GOAT (Figure 1). GOAT's structure is highly conserved among species (Lim et al., 2011) and its mRNA expression pattern in the body resembles that of ghrelin (Romero et al., 2010). GOAT activity is required for octanylation of ghrelin and is specific for ghrelin only (DAMDINDORJ et al., 2012). The attention to GOAT has recently increased in the ghrelin field. In fact, in addition to its central actions (Banks, Tschop, Robinson, & Heiman, 2002), there is now robust evidence that acyl-ghrelin acts on appetite and food intake via peripheral pathways. For example, GHS-R1a's are located on vagal afferent soma (Date et al., 2002; Grabauskas et al., 2015) and ghrelin-induced food intake is blocked by vagotomy in rodents and humans (Inui et al., 2004; le Roux et al., 2005). Systemic ghrelin administration suppresses vagal afferent firing, and selective blockade of the gastric vagus nerve, either by capsaicin (afferent only) or surgical differentiation (afferent and efferent pathways), blocks c-Fos expression within the arcuate nucleus in response to ghrelin-induced feeding (Asakawa et al., 2001; Benso DH, St-Pierre et al., 2012; le Roux et al., 2005). These observations support that, by preventing acyl-ghrelin formation, GOAT inhibition may be a promising approach to block acyl-ghrelin effects mediated by indirect vagal and direct central mechanisms. Furthermore, GOAT inhibition increases DAG and decreases the acyl-to-total ratio. DAG was thought to be non-active, as it binds to GHS-R1a with 1000-fold lower affinity than acyl-ghrelin, and its putative receptor is unknown. It has now been shown that DAG may counteract some of the effects of acyl-ghrelin, e.g., DAG infusion lowers appetite and blood glucose, and enhances insulin secretion (Ozcan et al., 2014). Also, DAG infusion

PI Name: [name]., Ph.D., M.Sc.

Abbreviated Title: GOAT

Version Date: 09/25/2023

lowers acyl-ghrelin concentrations, which may be responsible for reduced appetite and improved glucose and insulin secretion (Monteiro, 2014).

3.7 GLWL-01: PHARMACOLOGICAL PROPERTIES AND SAFETY PROFILE IN PHASE 1 STUDIES

GLWL-01: We will test GLWL-01, a highly selective, potent reversible uncompetitive GOAT inhibitor. GLWL Research Inc. has conducted *in vitro* and *in vivo* rodent work and, notably, a first-in-human clinical study in healthy individuals. To our knowledge, GLWL-01 is the first GOAT inhibitor tested in humans. GLWL-01 inhibits human GOAT with an IC₅₀ of 192 nM in a primary enzyme assay and 8.20 nM in a cell-based assay. Toxicology and pharmacology studies support GLWL-01 safety. It is readily absorbed with oral bioavailability across distinct species ranging from 69% to > 100%; time to reach maximum plasma concentration is reached consistently within 0.5 hours after oral dosing in rats, dogs, and monkeys (*GLWL Research Inc., unpublished/confidential*). Based on PK data in healthy subjects, both renal clearance and hepatic metabolism are involved in the clearance of GLWL-01. Mean plasma elimination half-life values following oral dose administration ranged from 2 to 5.5 hours across different species.

PI Name: [name]., Ph.D., M.Sc.

Abbreviated Title: GOAT

Version Date: 09/25/2023

For additional details, please see the GLWL-01 Investigational Brochure (IB Version Date 17OCT2017).

Previous work with GLWL-01 in humans: The first-in-human study conducted by GLWL Research Inc. established the safety and tolerability of GLWL-01 up to 450 mg b.i.d. in humans; the same highest allowed dose will be used in our clinical study. This is also consistent with an ongoing clinical trial that GLWL Research Inc. is conducting in patients with Prader-Willi Syndrome (ClinicalTrials.gov NCT03274856). GOAT engagement was studied *in vitro* and *in vivo* in mice and humans. *In vitro* and *in vivo* mouse studies show that GLWL-01 dose-dependently reduces acyl-ghrelin and increases DAG concentrations. The first-in-human study also indicates that GLWL-01 up to 450 mg b.i.d. significantly and dose-dependently reduces acyl-ghrelin and increases DAG concentrations (GLWL Research Inc., *unpublished/confidential*). Specifically, administration of single GLWL-01 doses of up to 600 mg QD in healthy subjects, and of multiple (up to 28 days) GLWL-01 doses of up to 600 mg BID in obese patients with type 2 diabetes was safe and generally well tolerated (GLWL Research Inc., *unpublished/confidential*). Doses of GLWL-01 equal to or higher than 150 mg BID resulted in numerical decreases of plasma AG levels in obese patients with type 2 diabetes over 28 days, with the maximum decreases observed for the 450-mg BID dose group. Therefore, a 450-mg BID dosing regimen was chosen for this study as it has been demonstrated to be safe and to achieve target engagement. For additional details, please see the GLWL-01 Investigational Brochure (IB Version Date 17OCT2017).

3.8 INNOVATION

Since 2006, the preclinical and clinical literature on the role of ghrelin and its receptor in AUD has been exponentially increasing. As such, targeting the ghrelin receptor system to treat AUD is a highly innovative approach. Recent translational work conducted by the PI and his team indicate a role of ghrelin in alcohol-seeking behaviors (Farokhnia et al., 2018; [name] et al., 2014). The first translational step taken by the PI and his team toward medication development has been to block GHS-R1a as a novel target to treat AUD. Safety and preliminary behavioral work have been conducted (Lee et al., 2018) and additional human work is ongoing under our current protocol, 16-DA-0080. The increasing knowledge of the ghrelin system has highlighted the potential role of the GOAT enzyme as a novel approach to target the ghrelin system. Therefore, this protocol is highly innovative as it represents the first attempt to test in humans the potential role of GOAT inhibition in AUD.

4 STUDY OBJECTIVES:

We propose to test the GOAT inhibitor GLWL-01 as a novel treatment for AUD. This will be a Phase 1b / 2a, proof-of-concept (early-signal) human laboratory study with GLWL-01 (450 mg b.i.d.).

GLWL-01 and matched placebo are provided by GLWL Research Inc. under a fully-executed NIH CRADA.

4.1 Primary outcome measures:

The co-primary aims will be to determine:

- 1) Whether the number of adverse events (AEs) experienced differ in the GLWL-01 condition, compared to placebo

PI Name: [name]., Ph.D., M.Sc.

Abbreviated Title: GOAT

Version Date: 09/25/2023

- 2) Whether GLWL-01, compared to placebo, reduces alcohol cue-elicited craving using a validated alcohol cue-reactivity procedure.

4.2 Secondary outcome measures:

The secondary aims will be to determine:

- a. Whether GLWL-01, compared to placebo, reduces food choices in a “virtual buffet” conducted in a virtual reality context.

Additional outcomes measures:

- b. We will also monitor behavioral assessments of pain, anxiety, depression, alcohol craving and withdrawal, and smoking.
- c. We will also monitor weight as well as food intake via a food intake

5 STUDY DESIGN AND METHODS

5.1 Overview

This study is aimed to test GLWL-01 450 mg b.i.d. for safety and an early-signal of efficacy in treating AUD.

5.2 Design

A within-subject, counterbalanced, double-blind, placebo-controlled study using GLWL-01, in individuals with AUD. Subjects will be randomized to the order of the study drug condition (GLWL-01 and then placebo; or placebo and then GLWL-01) using a block randomization based on the following two variables: sex and smoking status. Associate Investigator [name]., will develop the block randomization grid which will be sent to the NIDA IRP Pharmacy staff. No other members of the study team will have access to the block randomization grid.

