1994). The scale is divided into 4 subscales: BAS Drive, BAS Fun Seeking, BAS Reward Responsiveness, and BIS. Research suggests these systems play an important role in vulnerability to addiction. The individual differences in reward sensitivity measured by these scales are especially relevant to addiction when examining the role of the DA reward system. The goal of this assessment in the current study is to further explore how BAS and BIS personality traits relate to alcohol craving and the activation of reward circuitry.

d) Virtual Buffet Questionnaires: The following questionnaires are assessments of individuals' attitudes and cognitions relating to eating and weight that have been linked with behavior change. These characterization measures may help to explain variations in subject behavior in aspects of the trial (e.g., the virtual buffet).

1. Perceived Family History: weight and alcohol problems (Eisenberg, Street, & Persky, 2017)
2. Implicit Theories of Weight, Alcohol Use and Eating (Burnette, 2010)
3. Causal Beliefs Scale for Alcohol Dependence and Casual Beliefs Scale for Body Weight (Link, Phelan, Bresnahan, Stueve, & Pescosolido, 1999; Moss-Morris et al., 2002)
4. Perceptions of Personal Control and Treatment Control (Broadbent, Petrie, Main, & Weinman, 2006)
5. Self-Stigma and Alcohol Dependence (Schomerus et al., 2011)
6. Perceptions of passing down propensity for disease (Persky, McBride, Faith, Wagner, & Ward, 2015)

f) Smoking. The high co-morbidity between alcohol and nicotine dependence reflects a strong connection between alcoholism and smoking (Littleton, Barron, Prendergast, & Nixon, 2007). We will assess the severity of nicotine dependence with the Fagerström Test for Nicotine Dependence (FTND; (Heatherton, Kozlowski, Frecker, & Fagerström, 1991)), cigarettes smoked before and then during the duration of the study (via the TLFB) and Breath CO levels, for possible exploratory analyses, which might guide future alcohol/smoking studies. We will be able to collect the precise number of cigarettes smoked during the inpatient stay via the smoking Timeline Follow Back. Furthermore, when experimental procedures will take place, smoking breaks will be standardized across and between subjects.

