7 STATISTICAL ANALYSIS

7.1 *Analysis of data/study outcomes*

Outcome data will be examined for homogeneity of variance, and if necessary transformed to meet this criterion. As this is a within-subjects design, repeated measures analysis of covariance (ANCOVA) will be used to analyze the primary outcome, with drug condition as the within-subjects factor. Similarly, for secondary outcome measures such as food choices, repeated measured ANCOVA will also be used.

Biomarkers and hormonal measurements, such as feeding-related peptides stress-related hormones and/or inflammatory markers (see Section G,1), will also be correlated with changes in primary and secondary outcomes to explore the relationship between hormonal responses of interest and behavioral changes. A probability level of 0.05 or lower will be considered significant.

Potential covariates will be evaluated such that covariates that significantly predict the outcome measure will be retained in the model. Negative affect, as measured by the POMS-2 and Symptom Checklist, and cannabis dependence, if present, will be entered as covariates of particular interest in analysis for primary and secondary outcome responses. Additional covariates include baseline characteristics, like age, race, years of education, alcohol drinking levels, ADS score, family history of alcoholism density and number of days of alcohol abstinence prior to enrollment.

7.2 *Power analysis*

We performed a power analysis for the primary outcome and it is consistent with: 1) our previous Phase 1b study (N = 12 completers) with PF-5190457, where the primary outcome was the number of AEs experienced differ in the drug condition, compared to placebo; and 2) effect sizes ($dz = 0.5$) of alcohol cue-reactivity studies for other medications like the FDA-approved naltrexone and other experimental compounds (George et al., 2008; Miranda et al., 2014; Monti et al., 1999, 2000). The goal will be to reach up to 34 completers. A sample size of 43 subjects will be needed: a) considering the following parameters: $dz = 0.5$, α err prob = .05, and power ($1 - \beta$ err prob) = .80 (see Table 1 for additional details); and b) considering an attrition rate of approximately 20%.

PI Name: [name]., Ph.D., M.Sc.

Abbreviated Title: GOAT

Version Date: 09/25/2023

Table 1: Power Analysis

t tests - Means: Difference between two dependent means (matched pairs)

[figure not shown]
Analysis: A priori: Compute required sample size

Input:

Tail(s)	= Two

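### The craving and buffet models name no period, sequence or stratification term, although treatment order is randomised within sex and smoking blocks; the test stays valid but gives up some power

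*Combined protocol and SAP*

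**What the plan says.** Section 5.2 describes a two-sequence crossover. Each participant is randomised to one of the two drug orders "using a block randomization based on the following two variables: sex and smoking status".

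Section 7.1 is the whole analysis plan. It specifies a repeated-measures ANCOVA "with drug condition as the within-subjects factor" for the primary outcome, and the same method for secondary outcomes such as food choices. No other factor is named. On covariates it says three things:

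- "covariates that significantly predict the outcome measure will be retained in the model".
- Negative affect and, if present, cannabis dependence "will be entered as covariates of particular interest in analysis for primary and secondary outcome responses".
- A further, open-ended list opens with: "Additional covariates include baseline characteristics, like age, race, years of education, alcohol drinking levels, ADS score". It goes on to family-history density and days of abstinence before enrolment.

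Sex and smoking status are not in these lists. Among the subject characterisation measures in section 5.4, smoking severity, cigarette counts and breath CO are collected "for possible exploratory analyses, which might guide future alcohol/smoking studies".

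Section 7.2 sizes the trial with a paired t-test at dz = 0.5, a value taken from effect sizes "of alcohol cue-reactivity studies for other medications like the FDA-approved naltrexone" and other compounds.

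**The concern.** The order of treatment is what was randomised, and it was balanced within sex and smoking blocks. An analysis that follows this design would carry period and sequence, and would fix the blocking factors in advance. The plan names none of the four. It also leaves unlisted covariates to a significance rule, so even if sex and smoking status were screened, they could be dropped on a p-value.

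The stake is precision. Participants stay in an inpatient unit for about 14 days and go through the same cue exposure twice. Craving may therefore drift between stages whatever the drug. If it does, a drug-only model treats the drift as noise. If it drifts differently in smokers and non-smokers, or in men and women, that difference is treated as noise too. The planned power of 0.808 is less than one percentage point above the 0.80 target, so there is little room to lose.

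**Working it through.** **Inputs from section 7.2, Table 1 and section 7.3:** dz = 0.5, two-sided alpha 0.05, paired t-test, 34 completers, about 20% attrition.

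**The plan's own figures.** Noncentrality = 0.5 × √34 = 2.9155. Critical t on 33 df = 2.0345. Power = 0.8078. Enrolment = 34/(1 − 0.20) = 42.5, rounded up to 43. All agree with the protocol.

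**Stratum main effects.** Sex and baseline smoking status are constant within a person, so they drop out of the drug-minus-placebo difference. In one simulated data set of 34 complete pairs with large sex and smoking effects, the drug estimate was −0.4197 and its SE 0.1900, both with and without those main effects.

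**What does not drop out.** Scale the residual SD of the paired difference to 1 and write

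d = δ + s × [π + γ₁(sex − p₁) + γ₂(smoking − p₂)] + e,

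where s = +1 or −1 by sequence, π is the common Stage 1 to Stage 2 shift, γ₁ and γ₂ are the differences in that shift between the levels of each stratum, and p₁ and p₂ are the stratum proportions. If these terms are left out, the residual variance grows by about π² + Σγ²p(1 − p).

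**Closed-form approximation, 34 completers, 50:50 strata for the γ rows:**

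| Assumed effect | Added variance | dz becomes | Power |
|---|---|---|---|
| π = 0.3 | 0.3² = 0.09 | 0.5/√1.09 = 0.479 | 0.774 |
| π = 0.5 | 0.5² = 0.25 | 0.5/√1.25 = 0.447 | 0.716 |
| one γ = 0.5 | 0.25 × 0.25 = 0.0625 | 0.485 | 0.784 |
| both γ = 0.5 | 2 × 0.0625 = 0.125 | 0.471 | 0.761 |

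These values are slightly pessimistic. Blocking keeps order nearly balanced, so the shift mostly enlarges the estimated SE rather than the true variability of the estimate.

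**Simulation with the blocking included** (blocks of 4 within sex by smoking; 35% female and 60% smokers assumed; 10,000 runs per setting), shown as type I error / power:

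| Assumed effect | Drug only | + period | + period and period-by-stratum |
|---|---|---|---|
| none | 0.050 / 0.816 | 0.050 / 0.816 | 0.050 / 0.808 |
| π = 0.3 | 0.041 / 0.781 | 0.050 / 0.807 | 0.049 / 0.801 |
| π = 0.5 | 0.030 / 0.730 | 0.046 / 0.810 | 0.045 / 0.806 |
| both γ = 0.5 | 0.040 / 0.772 | 0.041 / 0.773 | 0.052 / 0.803 |
| π = 0.5 and both γ = 0.5 | 0.026 / 0.699 | 0.040 / 0.773 | 0.050 / 0.803 |

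The Monte Carlo SE of a power near 0.81 is √(0.81 × 0.19/10,000) = 0.004, so 0.816 lies about two standard errors above the exact 0.808. Repeat simulations gave 0.79 and 0.74 for π = 0.3 and 0.5. For a single γ = 0.5, simulated power was 0.79 to 0.80. For both, it was 0.77 to 0.78.

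**Cost if nothing is there.** From 33 to 32 error df, power goes from 0.8078 to 0.8070. At 29 df it is 0.804. In the simulation, the three period terms took 0.816 to 0.808.

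**The case against.** The strongest reply is that this is a crossover. Each participant is their own control, so the usual parallel-group reason for adjusting for stratification factors largely does not carry over. That stands: sex and smoking main effects do nothing for complete pairs. Participants with one stage would carry between-person differences, but only if the model keeps them. With 43 − 34 = 9 such participants, and assumptions about within-person correlation and stratum strength, modelling the strata would cut the variance by only about 0.3 to 1.1%.

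A second reply also stands. The covariate list in 7.1 is illustrative and other covariates may be evaluated. A reader might infer that sex and smoking status are shut out of the analysis. The text supports only that they are unspecified, with no guaranteed place.

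Third, no passage gives or implies a period effect on craving, or one that differs by stratum, and standardised smoking breaks on experimental days may limit the smoking mechanism. This is fair, and every power loss above is therefore conditional. It does not remove the case for the period term, which costs almost nothing if there is no period effect. It does weaken the case for the stratum-by-period interactions, which are a matter of preference in a 34-completer proof-of-concept study.

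**Conclusion.** The gap is real and modest. As written, section 7.1 leaves period variation, and any stratum-specific period change, in the error term, so the drug test is conservative. The period term matters most: power of about 0.78 to 0.79 with a common shift of 0.3 SD and 0.73 to 0.74 with 0.5 SD, against about 0.81 with the term in the model. The strata matter less: about 0.78 to 0.80 if one has a 0.5 SD difference in shift, and about 0.76 to 0.78 if both do.

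These figures rest on assumed effect sizes, block size and stratum proportions that the documents do not give.

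A reader might infer that a trial stratified this way and analysed without its strata gives a biased or anti-conservative result, or is undersized. The documents do not support that. Order is counterbalanced, the drug-only test had type I error between 0.026 and 0.050 in every setting tabulated, and 34 completers and 43 enrolled still follow from the stated inputs.

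**What to change.** In section 7.1, for the cue-elicited craving and virtual-buffet outcomes, pre-specify drug, period and sequence as fixed terms. Add sex and baseline smoking status as design terms, and state that none of these is subject to the significance-based retention rule. As a small optional addition, include the interactions of sex and smoking status with period, with both variables centred so that the period term keeps its meaning as an average shift.

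This takes one sentence of analysis wording. Both stratum variables must be known to randomise, and stage and order are recorded by design, so no new data are needed. The price is a few error degrees of freedom, at most about 0.01 in power if no period or stratum-by-period effects exist. Sample size is unchanged.

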5.3 Screening

The initial screening process for this protocol is conducted under the 06-DA-N415 , “Evaluation of potential research subjects – screening protocol for clinical studies” (hereto referred to as the screening protocol). This is a protocol led by the Office of the Clinical Director (OCD) at the National Institute on Drug Abuse Intramural Research Program (NIDA IRP) to assess potential research participants’ eligibility for entering all protocols at the NIDA/IRP. Additional details can be found in the screening protocol documents. As routinely done at the NIDA IRP, the screening procedures and data collected under the screening protocol will capture information above and beyond that which is necessary to determine eligibility for this protocol but allows the Investigators to assess the eligibility criteria for this protocol.

If suitable, subjects will be offered to participate in this protocol. If subjects agree and sign the consent form, they will be enrolled in the study and start the study procedures.

Once enrolled participants may undergo an additional screening process if they leave the inpatient unit between Stages 1 and 2 after being granted temporary leave due to personal emergencies or extenuating circumstances (see Overview). Upon returning to the inpatient unit after the temporary leave, they will

PI Name: [name]., Ph.D., M.Sc.

Abbreviated Title: GOAT

Version Date: 09/25/2023

undergo a standard search procedure required by the inpatient unit and an alcohol and drug screening to determine if there are any changes to their eligibility status. A positive BAC or urine during screen that is positive for any of the following substances: benzodiazepines, barbiturates, cocaine metabolites, morphine, oxycodone, methadone, amphetamine, and / or buprenorphine may result in an extension of the wash-out window until they are able to provide a negative urine drug screen and BAC or termination of study participation and not move forward to the Stage 2 based on the clinical judgement of the MAI and PI. The urine drug screening also includes testing for THC/cannabis however this is not an exclusion criterion for this study nor will it result in termination study. The reason why information on cannabis use is collected is because, consistent with the initial drug screening, if cannabis use is detected it will be assessed and entered a covariate in the data analysis.

The inpatient unit is operated and managed by Johns Hopkins Institute for Clinical and Translation Research (ICTR) and has standardized search procedures for any person staying on the unit. This search procedure is to prevent any items that are prohibited or illegal from entering the unit. If any prohibited items are found during the search procedure, the study team will be informed, and the items will be confiscated per ICTR policy. This will not result in the termination of study participation.

5.4 Overview:

Eligible participants will undergo Stages 1 and 2, where study drug (GLWL-01 or placebo) administration will be counterbalanced. A study drug wash-out window of at least 2 days will take place between Stage 1 and Stage 2. During each Stage, subjects will take the study drug twice a day (b.i.d.) for a minimum of 4 days to allow flexibility, maximize feasibility and minimize scheduling problems. At the end of each Stage, the last evening dose of the study medication will not be administered. As part of this study, subjects will be admitted to an inpatient facility (Clinical Research Unit (CRU)) on the Johns Hopkins Bayview Medical Center (referred to as either Bayview or JHBM) campus and will remain as inpatients for the duration of the two Stages and the wash-out window for an inpatient stay of approximately 14 days. We allow some flexibility to accommodate patient and CRU scheduling needs with a maximum possible 21-day length of total number of inpatient stays allowed. As for many other NIDA clinical protocols, study procedures take place either in the Bayview CRU or the NIDA IRP Biomedical Research Center (BRC) building which are both on the Bayview campus in Baltimore, MD. Participants may only leave the CRU during the wash-out window for personal emergencies and extenuating circumstances pending the approval of the PI, MAI or other covering health care provider who will evaluate the pass request and determine whether the pass may be granted. Participants on approved leave during washout do not receive remuneration while on leave and the total number of days on leave do not count toward the 21-day ceiling of stay in our clinical facilities during their participation in this study.

When the participant returns to the CRU after the temporary leave, they will undergo the standard CRU participant search procedure and alcohol and drug screening. A positive BAC or urine drug screen that is positive for any of the following substances: benzodiazepines, barbiturates, cocaine metabolites, morphine, oxycodone, methadone, amphetamine, & buprenorphine may result in an extension of the wash-out window until they are able to provide a negative urine drug screen and or negative BAC or may

PI Name: [name]., Ph.D., M.Sc.

Abbreviated Title: GOAT

Version Date: 09/25/2023

result in termination of study participation and not moving on to the Stage 2 based on the clinical judgement of the PI and MAI. The urine drug screening is identical to the initial drug screen used in the screening procedure and it also includes testing for THC/cannabis however this is not an exclusion criterion nor will it result in termination study. Consistent with the initial drug screening, if cannabis use is detected it will be assessed and entered a covariate in the data analysis. After the inpatient stay, one outpatient follow-up visit in the clinic will be scheduled approximately a week after the discharge (the exact date may vary a little, based on the patient's schedule) to repeat the blood liver panel.

The following research procedures (1-3 listed below) will take place once in Stage 1 and once in Stage 2. These procedures will be the same for Stage 1 and Stage 2. Furthermore, beginning of study procedures may be delayed or participant may be withdrawn from the study for any clinical concerns (for example, clinically relevant severe alcohol withdrawal and/or any other clinical condition requirement immediate medical care).

These study procedures are similar to our ongoing protocol 16-DA-0080, therefore we will be able to compare the potential effects of GLWL-01 versus PF-5190457.

